**Comparison of glimepiride, alogliptin and
alogliptin+pioglitazone combination in poorly
controlled type 2 diabetic patients
(Protocol: Takeda_ALO-IIT)**

Version No: 3.3 date:29/Dec/2016

Principal Investigator's Affiliation: Seoul National University Bundang Hospital

Principal Investigator's Name: [name]

Research Outline

Title of Research	Comparison of glimepiride, alogliptin and alogliptin+pioglitazone combination in poorly controlled type 2 diabetic patients
Principal Investigator	[name] [name]
Institution Supporting Research Expenses	Takeda Pharmaceuticals Korea Co. Ltd.

Research Objective	
The primary objective is to compare the change in HbA1c in week 24 in 3 treatment groups: the glimepiride monotherapy treatment group; the alogliptin monotherapy treatment group; the alogliptin - pioglitazone combination therapy treatment group.
 
 - The secondary objective is to compare the change in HbA1c in week 12 and fasting plasma glucose (FPG) in week 12 and 24 in the following 3 treatment groups over the course of 3 months (at the Baseline, in Week 12): (the glimepiride monotherapy treatment group, the alogliptin monotherapy treatment group, and the alogliptin - pioglitazone combination therapy treatment group). - Also, the change in parameters of glycemic variability assessed by CGM will be investigated. - Also, for a 6-month period, the average change in the lipid profile will be compared (Baseline, Week 12, Week 24). 		
Research Plan	
 • This trial is a three-armed, open label, random assignment trial. • The research subjects are patients who are first starting their treatment or patients who have failed with the metformin treatment and are changing their medication. They will be assigned to one of the following treatment groups: the glimepiride monotherapy treatment group, the alogliptin monotherapy treatment group, and the alogliptin - pioglitazone combination therapy treatment group • This trial is a prospective trial which will conduct surveys 6 times over the course of the 6 months in which each treatment group is administered drugs (Week -2, Baseline, Week 4, Week 12, Week 24, follow-up safety survey). • This trial is a multicenter clinical trial which will be conducted at more than 5 general hospital medical institutions in the vicinity of the capital. 		
Research Period	Date of IRB Approval –		

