- Heart failure, moderate to severe kidney injury (creatinine clearance of <50 mL/min prior to screening)
- Patients with chronic hepatitis, or hepatitis B or C (not including healthy carriers of hepatitis B) or a patient with liver disease (defined as cases in which the alanine aminotransferase, aspartate aminotransferase, alkaline phosphatase, or serum total bilirubin level is higher than 2.5 times the ULN)
- Hereditary complications, such as galactose intolerance, Lapp lactase deficiency, or glucose-galactose malabsorption (restricted to drugs including lactase)
- Cardiovascular disease or myocardial infarction; or a percutaneous transluminal coronary angioplasty or coronary artery stent nephrostomy within the past 6 months
- A serious cerebrovascular accident, stroke, or transient ischemic attack within the past 6 months
- Laser treatment for diabetic proliferative retinopathy
- A medical history of alcohol or drug abuse in the past 3 months
- A medical history of cancer in which remission could not be achieved within 5 years
- A medical history of bladder cancer or active bladder cancer
- Uninvestigated macroscopic hematuria
- Has experienced major surgery
- Breast feeding women, pregnant women, or premenopausal for whom pregnancy is possible are not suitable for participation in this trial
- External injury, acute infection, existence of or medical history of other chronic illness

Criteria for exclusion based on laboratory test results are as listed below.

- A fasting blood glucose (FPG) level of >239.6 mg/dL
- Systolic or diastolic blood pressure of >160 mmHg or >100 mmHg respectively
- A serum creatinine level of 1.5 mg/dL for men or 1.4 mg/dL for women
- An albumin/creatinine ratio of 2,000 mg/g
- A fasting triglyceride level of > 5.1 mmol/l (452 mg/dL)

3) Target Number of Subjects and the Basis for This Calculation

Statistical Analysis

After Week 24 of this trial, changes in the level of HbA1c among the 3 treatment groups will be compared, but the level of significance of the compared values of two treatment groups will be divided by 3 to correct for the level of significance of the 3 treatment groups. The number of sample collections

will be calculated using the value which is calculated for the comparison of alogliptin and alogliptin - pioglitazone combination therapy, as is presented below.

$$\frac{(Z_{\frac{\alpha}{2}} + Z_{(1-\beta)})^2 \times (\sigma_1^2 + \sigma_2^2)}{(\mu_1 - \mu_2)^2}$$

$\alpha = 0.05/3, 1 - \beta = 0.9$

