An adverse event (AE) is defined as the occurrence of an undesirable medical incident occurring in a clinical trial subject who has been administered drugs. It is not necessary for the treatment to have a causal relationship with the adverse event.

Therefore, an AE is any undesirable and unintended sign (e.g., abnormal laboratory test level findings), symptom, or chronic illness which correspond chronologically with the use of the corresponding pharmaceuticals regardless of whether it is determined to be related to the pharmaceuticals.

2. SAEs

All SAEs related to this treatment will be collected for this research protocol. An SAE is defined as a case in which the following undesirable medical incidents occur from an unspecified dose.

1. If death is caused.
2. If the situation is life threatening.

“Life threatening” will be used to describe instances in which the subject encountered the risk of death at the time of the incident. It will be used for cases which were more severe than had been anticipated and could have caused death.

3. If hospitalization or an extension to an existing hospitalization period is required.
4. If persistent or significant handicap/disability is caused.
5. If a congenital anomaly/birth defect is caused.
6. If it corresponds to a significant medical incident which satisfies the following:

Intervention may be necessary to prevent the above clauses 1 – 5.

Even though the corresponding event was not immediately life threatening, was non-fatal, or did not cause hospitalization, it could have put the research subject at risk.

The case described or an equivalent case is included in Takeda’s list of medically significant AEs.

3. Severity of AEs

The categories of intensity (severity) are as classified below:

Mild:	The case is temporary and the subject can easily endure it.
Moderate:	The case causes discomfort to the subject and causes a hindrance to daily life.
Severe:	The case causes a considerable hindrance to the subject’s daily life.

4. Collection and Reporting of Adverse Events of Special Interest

The trial investigator must report pancreatitis, hypersensitivity reactions including Stevens–Johnson Syndrome, hepatic effects, bladder cancer, and other related adverse events of special interest.

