
Bladder Cancer: Bladder Cancer is an adverse event of special interest of pioglitazone. The patient must quickly notify the investigator if macroscopic hematuria or other symptoms related to urination (dysuria or overactive bladder) occur while the corresponding drugs are being administered. If a bladder cancer diagnosis is confirmed, it must be reported to Takeda.

Bladder Cancer Withdrawal Criteria:
 
 - If there is a patient with a medical history of bladder cancer or unexplained hematuria, risk factors for bladder cancer (age, smoking history, exposure to some surgeries/chemotherapy (e.g., cyclophosphamide or radiation therapy of the pelvic region)) must be evaluated before the start of treatment. Whether or not macroscopic hematuria is present must be evaluated before treatment.

 - The patient must quickly notify the investigator if macroscopic hematuria or other symptoms related to urination (dysuria or overactive bladder) occur while the corresponding drugs are being administered. The administration of the corresponding drug must be suspended while additional examinations are done to make a diagnosis. - The investigator must fill out the sections related to AE/SAEs in the CRF. - If a definite diagnosis of bladder cancer is made, the administration of the corresponding drug must be permanently suspended.

- If the administration of the corresponding drug is suspended in the subject because of suspension criteria related to bladder cancer, it must be recorded as an AE along with the reason for the suspension.
- An early termination review must be conducted along with monitoring for subjects who were suspended.

5. Collection and Reporting of SAEs

In the event that an SAE occurs during the AE collection period after the consent form has been signed, it must be reported in accordance with the following procedures:

The trial investigator must immediately fill out and sign a Takeda SAE Report Form in English on the first day of the incident or within 1 business day of the date the investigator was notified of the incident. As much information as possible should be fully included on the form and the form must include a minimum of the following information:

A brief explanation of the case and the reason for categorizing the case as a serious event.
Subject identification number
Name of the trial investigator
Name of the trial drug
Evaluation of the causal relationship

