The SAE report form must be sent to the addressee listed below within 1 business day:

<Safety Report Emergency Contact Information>

Liaison: [name], Drug Safety Officer
Deputy Liaison: [name], Deputy Drug Safety Officer
Email: [contact]
[contact]
[contact]

After the AE collection period, any SAEs voluntarily reported to the investigator must be reported to Takeda.

6. Follow-up Survey of SAEs

If information which was unavailable at the time of the initial report is later obtained, the investigator must fill out the Follow-up Survey SAE Report Form or supply other written documents and promptly send via fax within 1 business day of receiving the information. If requested, a copy of any related data collected from the hospital records (e.g., ECGs, laboratory tests, discharge summary reports, autopsy results) must be sent to the corresponding address.

Follow-up surveys must be carried out until cases related to an SAE are resolved or until there is a permanent result. The deadline and procedure for the follow-up survey are the same as the deadline and procedure for the first report.

7. Safety Reports for Trial Investigators, IRBs or ECs, and Regulatory Authorities

Takeda or an appointee must report all relevant SAEs to the regulatory authorities, trial investigators, and the IRBs or ECs if applicable under the national regulations of the country in which the trial is being conducted. Further, if other safety issues are confirmed which are sufficient enough to significantly change the result of the risk-benefit evaluation of the trial drug or to require consideration of a change to the administration of the trial drug or the whole execution of the trial, Takeda or an appointee will fill out an expedited report about these issues.

Takeda or an appointee will report any unexpected SAEs which are potentially related to the trial drug in the expedited report. In accordance with all relevant laws and regulations, a copy will be sent to all relevant regulatory authorities, the trial investigators, and the IRBs or ECs. If it is affiliated with a clinical trial institution, a copy of the expedited report will be sent to the institution's IRB or EC.

8. SAEs Follow-up Survey

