- Descriptive statistics (mean and standard deviation) are used to describe continuous variables of baseline demographic and biochemical parameters, and counts with percentages are presented for categorical variables of baseline demographic and biochemical parameters.
- The efficacy and safety analyses were based on the full analysis set population consisting of all the patients who received the investigational drug at least once.
- The demographic characteristics of subjects were analyzed using ANOVA for the continuous variables and the chi-squared (χ^2) test for the categorical variables.
- Efficacy endpoints at week 12 and week 24 were analyzed using ANCOVA model with Bonferroni (baseline value as a covariate) for continuous variables and Pearson chi-square test adjusted by Bonferroni for categorical variables.
- Missing data, which is an unavoidable occurrence in prospective studies, will be substituted for using the last observation carried forward (LOCF) method.
- A p value <0.05 will be considered to indicate statistical significance and the SPSS (Statistical Package for Social Sciences) Version 25.0 will be used for statistical analysis

10. Measures for the Protection of Research Subject Safety

1) Fundamental Measures to Ensure Research Ethicality

The Declaration of Helsinki (Revised 2013) and the ICH-GCP will be followed.

IRB approval is scheduled to be received before the start of this research. At the start of research after IRB approval, the research objectives and process will be sufficiently explained to the research subjects. An examination consent form will be received from persons who understand these and voluntarily choose to participate.

Prior to the start of the trial, the trial investigator must acquire the written approval of the institutional review board of the relevant trial institutions and/or regulatory commissions regarding the conduct of the trial and must send a copy to Takeda ([contact]). If alteration of the trial is necessary, the investigator must acquire the written approval of the institutional review board of the relevant trial institutions and/or regulatory commissions regarding the conduct of the trial and must send a copy to Takeda ([contact]).

As the research relates to human subjects, the investigators must register this trial at clinicaltrials.gov and any other relevant institutions if necessary.

2) Research Subject Consent Process

<Research Subject Consent Process>

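### The SAE definition item limits collection to treatment-related SAEs, while the reporting item and the monitoring plan set no such limit; the sentence should be reconciled with them.

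*Protocol*

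**What the plan says.** The statements on SAE scope are all in the Protocol, section 9.

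- **6), Adverse Event, item 1 (Definition):** an adverse event needs no causal link. "It is not necessary for the treatment to have a causal relationship with the adverse event".
- **6), item 2 (SAEs):** the collection rule is "All SAEs related to this treatment will be collected for this research protocol".
- **6), item 5 (Collection and Reporting of SAEs):** the site's reporting duty is worded without a relatedness condition: "In the event that an SAE occurs during the AE collection period after the consent form has been signed, it must be reported". The minimum content of the report includes "Evaluation of the causal relationship".
- **6), item 5, closing sentence:** "After the AE collection period, any SAEs voluntarily reported to the investigator must be reported to Takeda".
- **8), Data Safety Monitoring Plan:** safety is checked at every visit, and findings that amount to an SAE go to the IRB. No relatedness condition is set.

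The Research Outline describes the design: "This trial is a three-armed, open label, random assignment trial". Section 9, 9) bases the safety analysis on all patients who took the investigational drug at least once and does not restrict it by relatedness.

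**The concern.** Item 2 is the first rule a site meets under the SAE heading, and it names a narrower set of events than item 5. A site that takes it as the collection rule could leave out an SAE it judges unrelated. A site working from item 5 would submit the same event. The protocol does not say which item prevails.

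Relatedness is judged by investigators who know the arm, and no blinded causality assessment is described. Used as a condition of entry, that judgement decides which SAEs are counted. Recorded as an attribute, it removes nothing from the data. With nine hospitals listed in section 2, different readings would also make SAE counts non-comparable between sites. A later analysis plan cannot recover events that were never collected.

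**Working it through.** The point is textual. The plan states no figure for SAEs that could be reproduced, so the check sets the statements side by side.

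| Place in the Protocol, section 9 | Step | Relatedness required? |
|---|---|---|
| 6), item 1 | Definition of an adverse event | No |
| 6), item 2 | Collection of SAEs | Yes |
| 6), item 5 | Site reports SAE to sponsor | No; causality is a form entry |
| 6), item 5, closing sentence | SAEs volunteered after the collection period | No |
| 6), item 7 | Sponsor's expedited report of unexpected SAEs | Yes (potential relation to the drug) |
| 7) Suspension and elimination criteria | Elimination after an AE or SAE | No |
| 8) Data Safety Monitoring Plan | SAE findings to the IRB | No |
| 4), Table 1 | AE check at every visit and at the 30-day follow-up | No |

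1. **Do the rules conflict?** Item 2 read as the full extent of collection and item 5 cannot both describe what a site does with an SAE judged unrelated. Item 5 asks for a causality evaluation on each report, which has little purpose if only related SAEs arrive.

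2. **Is a relatedness filter at the site consistent with the rest?** No. Item 7 applies such a filter to the sponsor's expedited reports, a step that presupposes the SAEs have already reached the sponsor. Item 2 would put a filter ahead of that step. It would also make the rule narrower during the collection period than after it, when any volunteered SAE must be passed on.

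3. **When is an event lost?** Let N be the number of SAEs, s the share that occur at sites acting on item 2 alone, and r the share of those judged related. SAE reports lost = N × s × (1 − r). If every site follows item 5, s = 0 and the loss is 0. The Protocol gives no value for N, s or r, so the formula shows the condition for a loss but not its size.

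4. **What would still be on record?** Even at a site acting on item 2, an unrelated SAE meets the definition of an adverse event in item 1 and falls under the visit-by-visit AE check. The likely loss is therefore its identification and reporting as serious, rather than every trace of it.

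**The case against.** The strongest reply is that item 2 only introduces a definition, while item 5 carries the procedure and is unconditional. Item 2 says related SAEs are collected; it does not say that others are not. Collecting every SAE satisfies both items, and omitting unrelated ones breaches item 5. The monitoring plan, Table 1 and the elimination criteria would each bring an unrelated SAE to light. The narrow phrase may also be loose translation.

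Most of this stands. It shows that full collection is the better reading and that a site complying with item 5 loses no SAE report. It does not remove the defect, because a sentence stating a collection rule should not need five other places to correct it.

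Three stronger readings are tempting, and the documents do not support them:

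- **That the trial chose related-only collection.** Item 5 and the monitoring plan contradict this.
- **That most SAEs would go uncollected.** This needs an SAE rate, a share judged related and a share of sites following item 2, and none is given.
- **That a safety signal in the alogliptin or pioglitazone arms would be hidden.** Item 4 separately requires reporting of pancreatitis, hypersensitivity reactions, hepatic effects and bladder cancer, without a causality test. The protocol also names no formal between-arm test of SAEs.

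**Conclusion.** The inconsistency is real and minor. One sentence limits SAE collection to related events, several others do not, and no statement settles which scope governs the data. The consequence is conditional: SAEs are lost only at a site that acts on the item 2 sentence, and there inclusion rests on a relatedness judgement made with the arm known. The size of any loss cannot be derived from the document, and it is zero if every site follows item 5. The conclusion assumes only that investigators may act on the item 2 sentence as written. The point is worth correcting because it concerns an instruction to sites, which later analysis cannot repair.

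**What to change.** Reword the sentence in section 9, 6), item 2 to state that all SAEs occurring in the AE collection period after consent are collected regardless of causal relationship, with the investigator's causality assessment recorded as an attribute of each event. This brings item 2 into line with items 1 and 5 and with the Data Safety Monitoring Plan. The relatedness criterion in item 7 can stay, since it concerns the sponsor's expedited reports.

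The cost is one sentence in an amendment and a note to sites. Sites already following item 5 have no extra work; any site that had followed item 2 would complete a few more report forms at most. No treatment, dose or stopping rule is affected.

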information to determine the cause, there are post market reports of fatal and non-fatal hepatic failure in patients who took NESINA [reference Adverse Drug Events (6.2)]. In a randomized, controlled trial, an increase in the of the serum alanine aminotransferase (ALT) of 3 times the upper limit of normal (ULN) was observed in 1.3% of patients receiving alogliptin treatment and 1.5% of the patients in all control drug treatment groups. Type 2 diabetes patients can suffer from fatty liver disease, which can cause abnormal findings in hepatic function tests. These patients can also have other forms of liver disease and most of these cases of liver disease can be cured or managed. Therefore, it is recommended that the results of the hepatic function test be collected and that the patient be evaluated before starting

NESINA treatment. In patients with abnormal hepatic function test findings, extreme care must be taken when starting NESINA treatment. A hepatic function test should be run promptly if there is a patient with symptoms which could indicate liver damage (including fatigue, loss of appetite, abdominal discomfort, dark urine, or jaundice). In this clinical context, if it is confirmed that the patient has a clinically significant increase in the levels of hepatic enzyme or that the hepatic function tests continue to show abnormal findings or have worsened, NESINA treatment must be suspended and an investigation into the possible causes must be conducted. If there are no other explanations for the abnormal hepatic liver function test findings, the patient may not restart treatment with NESINA.

4) Use of Medication Known to Cause Hypoglycemia: Insulin and insulin secretagogues (e.g., sulfonylureas) are known to cause hypoglycemia. Therefore, a smaller dose of insulin or insulin secretagogues must be used to reduce the risk of hypoglycemia when these drugs are taken in combination with NESINA.

5) Macrovascular Outcomes: There are no clinical trials which show conclusive evidence of how to reduce macrovascular risks when NESINA or other diabetes treatments are administered.

- Precautions for Pioglitazone

Actos must be used with caution in the following patients:

- 1) Combination therapy with other oral hypoglycemic agents
- 2) Premenopausal women
- 3) Edema

7) Suspension • Elimination Criteria

Subjects with a drug compliance of less than 80% will be eliminated.

Subjects with an HbA1c level of more than 9.0% in Week 12 will be eliminated.

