Subjects who sign the trial subject consent form and participate in the trial but do not finish will be eliminated. The elimination of a subject can be determined at any time during the trial. Withdrawal of consent by the subject will also be considered as an elimination and the reason for the withdrawal of consent must be clearly recorded. Furthermore, if an adverse event and/or a serious adverse event occurs during the trial, the corresponding subject will be immediately eliminated from the trial.

8) Safety Evaluation Criteria (Including Side Effects), Evaluation Methods, and Reporting Methods

Data Safety Monitoring Plan (DSMP)

According to existing research results, this trial is expected to be low risk because of the possibility and

severity of risk and discomfort which could occur in this in trial. The principal investigator is planned to continuously monitor for this risk and discomfort. Safety monitoring for this research will be conducted during every visit through an oral interview, a physical exam, laboratory tests, *et cetera*. If any of these results correspond to an SAE, it will be reported to the IRB.

- If there are any deviations from the protocol, the investigator will report major deviations to the IRB within 15 days of the point at which he or she becomes aware of the deviation and if there are minor deviations, the investigator will gather incidents of minor deviations and report them to the IRB at least once a year.
- Adverse events and all other information relating to safety will be reported in a safety information summary report. If there are incidents related to safety, a summary of the accumulated non-individual data should be compiled and reported at least once every 6 months in the form of a summary.

- Cases related to danger to the research subjects or other persons in which the case is judged to be an unexpected problem or in which it is life threatening should be reported to the IRB within 7 days and within 15 days for all other cases.
- The principal investigator or the subinvestigator will collect data and safety information, examine major efficacy evaluation endpoints, and conduct continuous monitoring every 6 months after the start of research.

9) Data Analysis and Statistical Analysis Methods

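### SAE criterion 2 explains "life threatening" by two unreconciled tests, one of which brings expectedness into seriousness and can affect the 7-day IRB deadline (minor)

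*Protocol*

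**What the plan says.** Protocol section 9, 6), Adverse Event, item 2 lists six criteria for an SAE. Criterion 2 is a life-threatening situation, and two consecutive sentences explain it.

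- The first says that the term is used to "describe instances in which the subject encountered the risk of death at the time of the incident".
- The second says: "It will be used for cases which were more severe than had been anticipated and could have caused death".

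Two other criteria can also make such an event serious. Criterion 3 reads: "If hospitalization or an extension to an existing hospitalization period is required". Criterion 6 covers a significant medical incident and gives three lines: a need for intervention to avert one of the earlier outcomes; an event that "was not immediately life threatening, was non-fatal, or did not cause hospitalization, it could have put the research subject at risk"; and inclusion on the sponsor's list of medically significant events. It does not say whether one line is enough or all three are needed.

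Expectedness appears in two other places. Under item 7 of the same section, the sponsor or its appointee "will report any unexpected SAEs which are potentially related to the trial drug in the expedited report". In section 9, 8) (Data Safety Monitoring Plan), the rule for cases involving danger to subjects or others says that those where "the case is judged to be an unexpected problem or in which it is life threatening should be reported to the IRB within 7 days"; the remaining cases have 15 days.

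**The concern.** Seriousness asks what the event did to the patient. Expectedness asks whether it was foreseen. The protocol keeps the two apart in its reporting rules, but the second sentence of criterion 2 merges them. It also replaces an actual danger with one that might have arisen.

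The protocol gives no reference for what severity counts as anticipated. The mild, moderate and severe scale in item 3 does not supply one. Investigators at the nine listed sites would each have to decide, and could apply the criterion differently.

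What is at stake is the consistency of one SAE criterion and the IRB deadline that uses the same term. That deadline turns on whether a case is life threatening, not on whether it is an SAE. An event that stays serious through another criterion can therefore still be given the longer deadline.

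**Working it through.** No figure in the protocol needs reproducing and no arithmetic applies. The check applies the definition and the IRB rule together to each kind of event.

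Inputs:

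- **R**: the patient was actually in danger of dying when the event occurred (first sentence, section 9, 6), item 2).
- **X**: the event exceeded anticipated severity and might have been fatal (second sentence, same place).
- **IRB rule** (section 9, 8)): 7 days if the case is an unexpected problem or life threatening; otherwise 15 days.

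The text allows two readings:

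- *Extension*: life threatening = R or X.
- *Condition*: life threatening = R and X.

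| Event | Extension reading | Condition reading |
|---|---|---|
| R yes, X no (real danger, anticipated severity) | Life threatening; 7 days | Not life threatening; probably not an unexpected problem either; 15 days |
| R yes, X yes | Life threatening; 7 days | Life threatening; 7 days |
| R no, X yes (no real danger, worse than anticipated, might have been fatal) | Life threatening; 7 days | Not life threatening; may still have 7 days as an unexpected problem |

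Three results follow.

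1. The move from 7 to 15 days occurs only in the first row and only under the condition reading. Under that reading an event needs surprising severity to count as life threatening. The life-threatening trigger, which the IRB rule lists as an alternative to the unexpected-problem trigger, then adds almost nothing to it.
2. Over-inclusion occurs in the third row under the extension reading. Its effect on timing is small, because an event worse than anticipated may reach 7 days as an unexpected problem anyway. What changes is the label.
3. Loss of SAE status needs more than the condition reading. The event must also fail criteria 1 and 3 to 6. Hospitalisation alone keeps it serious. Criterion 6 would normally do so too, unless its three lines are taken as joint conditions, which the text leaves open.

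The comparison with item 7 of section 9, 6) points the same way. There, being unexpected selects among events already classed as SAEs. It is not part of what makes them serious.

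**The case against.** The strongest reply is that the two sentences need not conflict. Read as alternatives, the second only widens the term, so no event is lost or delayed. That is a fair reading, and it is why the sentences are better called unreconciled than incompatible. It does not settle the matter: the text does not choose a reading, and the wider one labels events life threatening when no life was in danger.

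A second reply is that the IRB rule in section 9, 8) does not refer back to the definition, so the term could be taken there in its ordinary sense. That is possible, but the only explanation the protocol gives is the one in section 9, 6), and a site would reasonably use it.

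A reader might infer more: that the same event would be serious in one arm and not in another, because the trial is open label and the protocol says "Insulin and insulin secretagogues (e.g., sulfonylureas) are known to cause hypoglycemia". The documents do not support this.

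- The definition names no arm and no drug-specific standard of anticipation.
- The hypoglycaemia sentence is a precaution about combining such drugs with alogliptin. It concerns occurrence, not life-threatening severity on glimepiride alone. The hypothesis in section 6 calls that arm low dose, and section 9, 8) expects the trial to be low risk.
- Pancreatitis and hypersensitivity must be reported as events of special interest (section 9, 6), item 4). Symptoms listed in the precautions, which include hypoglycaemia, must also be reported and followed up. Neither rule depends on seriousness.
- The protocol specifies no test of SAE counts between arms, so no stated comparison would change.

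A reader might also infer that the 1-business-day report to the sponsor would be missed. That report applies to every SAE under any criterion, so it is lost only if all the criteria fail.

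**Conclusion.** The point holds as a minor defect of definition. Criterion 2 sets two tests that are not reconciled, and the second brings anticipated severity and a hypothetical outcome into a judgement of seriousness.

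The practical effect is narrow. Under the condition reading, an event with real danger to life but of anticipated severity can move from the 7-day to the 15-day IRB deadline. This assumes that the site applies the section 9, 6) explanation when using section 9, 8), and does not otherwise judge the case an unexpected problem. Under the extension reading, some events are labelled life threatening without any real danger. The documents give no rate for either kind of event, so the number affected cannot be estimated.

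Bias between arms, a changed SAE comparison and a missed sponsor report are not established. No efficacy endpoint, sample size or error rate is affected.

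**What to change.** In section 9, 6), item 2, delete the second explanatory sentence. Alternatively, replace it with wording such as: *The term does not include an event that could have been fatal only if it had been more severe. Whether the event was anticipated plays no part in judging seriousness.* Leave expectedness where it already works, in item 7 and in the IRB rule of section 9, 8).

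In criterion 6, state that any one of the three listed conditions is sufficient. This removes doubt about whether it serves as a backstop.

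The cost is a short amendment and a notice to sites, with possibly small changes in how some events are classified. No extra patients, visits or tests are needed.
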